3. STUDY DESIGN

General Description

This will be a randomized, single dose, double-blind, placebo-controlled, Latin-square design with 5-period (full) crossover study with subjects randomized to treatment sequences. Subjects will complete all 5 Periods within the treatment sequence that they are randomized to.

The treatments are:

- Treatment A: Lasmiditan 50 mg
- Treatment B: Lasmiditan 100 mg
- Treatment C: Lasmiditan 200 mg
- Treatment D: Alprazolam 1 mg
- Treatment E: Placebo

Subjects will be randomized equally into one of ten treatment sequences:

Treatment Sequence	Period 1	Period 2	Period 3	Period 4	Period 5
1	A	B	E	C	D
2	B	C	A	D	E
3	C	D	B	E	A
4	D	E	C	A	B
5	E	A	D	B	C
6	D	C	E	B	A
7	E	D	A	C	B
8	A	E	B	D	C
9	B	A	C	E	D
10	C	B	D	A	E

Each Period including washout will be approximately 7 days in duration.

Study drug will be administered by site staff on Day 1 of each Period. Subjects will wear a blindfold when taking each dose to maintain the blind. The tablet size and shape are deemed similar enough to maintain the blind with a blindfolded subject.

CRCDS-MiniSim testing is conducted 1.5 hours post-dose (on Days 1, 7, 14, 21, and 28).

Schematic of Design:

Period 1 → Washout 1 → Period 2 → Washout 2 → Period 3 → Washout 3 → Period 4 → Washout 4 → Period 5 → EOS
 Day 1 Days 2-6 Day 7 Days 8-13 Day 14 Days 15-20 Day 21 Days 22-27 Day 28 Day 35

A sufficient number of subjects will be enrolled to complete 80 healthy volunteers in the 5-period crossover study.

The positive control (alprazolam 1.0 mg) is included to establish the sensitivity of the study endpoints to detecting residual sedation.

The total duration of study treatment for a participant will be approximately 5 weeks. The total duration of study participation will be in the range of 5-9 weeks depending on the duration of the screening period.

Study procedures

For complete details on the study assessments to be performed for the study, refer to [Appendix A](#).

Randomization and Unblinding Procedure

Prior to dosing, subjects will be randomly assigned to one of ten treatment sequences and dosed with study medication (lasmiditan, alprazolam or placebo) based upon a randomization scheme provided by Algorithme Pharma. Only the qualified person(nel) assigned to prepare and administer the study treatment will have access to the randomization schedule and dispensing records during the study period.

Subjects will wear a blindfold when taking each dose to maintain the blind. The tablet size and shape are deemed similar enough to maintain the blind with a blindfolded subject. Dosing will be observed by a study staff member (qualified party dispenser); no other study personnel will be present at the time of dosing.

4. STUDY ENDPOINTS

Primary Endpoint

The primary endpoint for this study is simulated driving performance as measured by SDLP using the CRCDS-MiniSim.

Secondary Endpoints

The secondary endpoints for this study include other measures of simulated driving performance, KSS and CogScreen SDC test.

- Sleepiness Endpoint – KSS
- Self-reported readiness to drive (“Right now do you feel safe to drive?”)
- Visual Analog Scales (VAS) to assess subject’s motivation and self-appraisal of their driving performance
- Performance Endpoints
 - CogScreen SDC test
 - Number of correct responses
 - Response Accuracy
 - Standard deviation of reaction time
- Driving Performance Endpoints
 - Lane exceedance; including number, maximum, duration, and area of exceedance
 - Ratio above speed limit, excessive speed count, excessive speed ratio
 - Average speed, speed deviation, speed count, speedings ratio
 - Excessive Ay (cornering speed threshold exceeded)
 - Collision count, off-road crashes, total collisions
 - DA: Correct Responses, Omission Errors, Commission Errors, Reaction Time, Standard Deviation of Reaction Times
- Single-dose plasma drug levels and driving performance

Safety Endpoints

Safety endpoints include:

- Adverse Events
- Clinical Laboratory Tests (hematology, chemistry, urinalysis)
- Vital Signs
- Physical examination
- Concomitant medication
- ECGs
- C-SSRS

The details of the safety endpoints’ assessment are presented in [Section 10](#).

Pharmacokinetic Endpoints

The pharmacokinetic endpoint for this study is plasma lasmiditan concentration data.

Sample Size Determination

This study is designed to test non-inferiority of lasmiditan doses relative to placebo, with an alprazolam test versus placebo to confirm the sensitivity of the simulator to detect treatment effects.

The following assumptions were made in the sample size computation:

- (a) within-subject standard deviation for SDLP is approximately 6 cm;

(b) the true difference between lasmiditan doses and placebo is 0;

(c) the non-inferiority (NI) margin is proposed to be 4.4 cm, which is the effect seen with 0.05% of blood alcohol content (BAC).

Under these assumptions, a sample of 80 subjects would provide in excess of 90% power to establish non-inferiority of any given dose of lasmiditan compared to placebo in terms of the primary end point, SDLP. This sample size is considered more than adequate to detect alprazolam differences from placebo, which are anticipated to exceed the NI margin.

5. ANALYSIS POPULATIONS

Safety Population:

All subjects who are treated with study medication will be included in the safety population. This population will be used for all demography, background and safety analyses.

Intent-to-treat (ITT) Population:

All subjects who are randomized and treated will be included in the ITT Population. This population will be used for efficacy analyses. Subjects will (in general) be included in all analyses for which data are non-missing.

Pharmacokinetics (PK) Population:

All subjects with evaluable PK data will be included in the pharmacokinetic population.

6. STATISTICAL METHODOLOGY

All analyses will be conducted using the SAS software, version 9.4, or higher

Adverse events and medical history will be classified using the standard MedDRA terminology version 19.1.

Prior and concomitant medications will be coded with the WHO-DDE dictionary version March 01, 2016.

In general, all summary tables will be presented for safety population. Summaries for adverse events will be presented by treatment.

In general, the data listings will include all enrolled subjects up to the point of study completion or discontinuation; exceptions will be listings pertaining to a subset of subjects only (e.g., subjects with blood sampling time deviations) or a subset of records/events (e.g., abnormal laboratory values).

Categorical variables will be summarized using the PROC FREQ procedure. Continuous variables will be summarized using the PROC UNIVARIATE, MIXED, and/or MEANS procedures. For log-transformed endpoints, geometric mean will also be presented.

The following general comments also apply to all statistical analyses and data presentations:

- Duration variables in days will be calculated using the general formula: (end date - start date) +1.
- Individual subject listings of all data represented on the CRFs will be provided to facilitate the investigation of tabulated values and to allow for the clinical review of all efficacy and safety parameters.
- When assessments are repeated for a given timepoint, only the result which is closest to the dosing time will be included in the summary tables.

The analyses described in this plan are considered a priori, that they have been defined prior to database lock. Any analyses performed subsequent to database lock will be considered post hoc and exploratory. Post hoc analyses will be labeled as such in the corresponding statistical output and identified in the clinical study report (CSR).

Analysis Time Points

Unless otherwise specified, the baseline value will be defined as the last non-missing evaluation prior to the first dose of study medication.

Methods for Handling Missing Data

No imputations of values for missing data will be performed. All data recorded on the case report form will be included in the listings that will accompany the CSR.

For subjects that have incomplete data within an assessment, data will be listed but not summarized and/or analyzed for that assessment.

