10.2 Study Periods

10.2.1 CRU Admission Days (Visits 2, 5, 8, 11, and 14: Days -1, 6, 13, 20, and 27)

Within 28 days after the Screening visit, eligible subjects will return for Period 1 (Visit 2). Subjects who meet the inclusion and no exclusion criteria will be instructed to return to the clinic on Day -1.

- A serum pregnancy test will be performed for all females of child-bearing potential upon admission to the unit.
- Continued subject eligibility will be verified, including serum pregnancy and screens for alcohol and drugs of abuse.
- The alcohol and drug screens will be repeated.
- A practice drive (approximately 20 minutes) will be performed on the driving simulator.
- A practice trial on the CogScreen SDC test.

- Vital signs will be measured.
- C-SSRS
- Any concurrent medication use will be recorded.
- Adverse Events (AEs) will be assessed.

Subjects will spend the night at the CRU.

10.2.2 Dosing Days (Visits 3, 6, 9, 12, and 15: Days 1, 7, 14, 21, and 28)

After a period of 8.5 hours in bed, subjects will be awakened. According to the randomization schedule, subjects will be assigned and dosed with study medication (lasmiditan, alprazolam, or placebo).

The following procedures will be performed:

- Pre-dose vital signs will be taken.
- A pre-dose pharmacokinetic (PK) blood sample will be taken (within 30 minutes before dosing).
- Subject will receive the study drug dose.
- Vital signs will be measured pre-dose and at 1.17 hours after dosing.

Approximately 1.25 hours after dosing, subjects will perform the CogScreen SDC Test and KSS, and indicate their self-perceived safety to drive.

Subjects will then perform the Country Vigilance-Divided Attention (CVDA) driving scenario on the CRCDS-MiniSim commencing approximately 1.5 hours post-dosing. Upon completion of the driving scenario subjects will be administered a VAS to assess subject's motivation and self-appraisal of their driving performance. The following procedures will also be performed:

- A post-dose PK blood sample will be taken approximately 155 minutes (-15 to +30 minutes) post-dose.
- AEs will be recorded.
- Any concurrent medication use will be recorded.

Subjects will leave the clinical site at approximately 24-hour post-dose. However, they will be advised to stay at the clinical site, if judged necessary by the physician in charge, for safety reasons.

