13.4.3 Vital Signs

Vital signs (BP, HR and body temperature) will be summarized by dose using descriptive statistics. Changes from baseline in vital signs will be summarized by descriptive statistics for each dose.

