For all vital signs, raw values, as well as the change from baseline, at each time point will be summarized by treatment, parameter and visit. Vital signs data will also be presented in a listing.

Subject listing of abnormal on-study vital signs values (Out-of-Range – Not Clinically Significant (NCS) or Clinically Significant (CS)) will be provided. Similarly, CS on-study vital signs values (Out-of-Range – CS) will be presented in a second listing.

Electrocardiogram

A triplicate 12-lead ECG will be obtained at time points throughout the study. In some cases, repeat abnormal ECGs may be obtained.

Raw values at each time point, as well as the change from baseline, will be summarized by sequence, parameter and visit and will also be presented in a listing.

A subject listing of abnormal on-study ECG assessments (Abnormal – NCS or Abnormal – CS) will be provided. Similarly, CS on-study ECG assessments (Abnormal – CS) will be presented in a second listing.

Physical Examination Findings

A physical examination will be conducted and results will be presented in a listing.

A subject listing of abnormal on-study physical examination results (Abnormal – NCS or Abnormal – CS) will be provided, including demographic information. Similarly, CS on-study physical examination results (Abnormal – CS) will be presented in a second listing.

Columbia-Suicide Severity Rating Scale (C-SSRS)

The Columbia-Suicide Severity Rating Scale (C-SSRS) is a suicidal ideation rating scale. The scale identifies behaviors and thoughts that are associated with an increased risk of suicidal actions in the future. The C-SSRS will be performed at Screening, on Days -1, 6, 13, 20, and 27, and Day 35 or EOS.

Subjects who answer 'Yes' to any of the questions on the C-SSRS questionnaire will be presented in a listing

Epworth Sleepiness Scale

The Epworth Sleepiness Scale assessment will be performed at Screening and results will be presented in a listing.

Simulator Sickness Questionnaire

A simulator sickness questionnaire will be performed at Screening and results will be presented in a listing.

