12. CHANGES TO PROTOCOL-SPECIFIED ANALYSES

There is no change from the planned analysis described in the protocol.

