APPENDIX A

STUDY SCHEDULES

Study Procedures	Screening (Within 28 Days Prior to 1st Dose) (Visit 1)	Period 1			Period 2			Period 3			Period 4			Period 5			Follow- Up/EOS
		Day- 1 (V2)	Day 1 (V3)	Day 2 (V4)	Day 6 (V5)	Day 7 (V6)	Day 8 (V7)	Day 13 (V8)	Day 14 (V9)	Day 15 (V10)	Day 20 (V11)	Day 21 (V12)	Day 22 (V13)	Day 27 (V14)	Day 28 (V15)	Day 29 (V16)	Day 35 (Visit 17)
Informed consent	X																
Medical/Social history	X																
Subject Eligibility	X	X			X			X				X		X			
Weight/Height ¹ (BMI)	X																X
Drug and alcohol screen	X	X			X			X				X		X			
Serum Pregnancy Test	X	X ⁹			X ⁹			X ⁹				X ⁹		X ⁹			X
Clinical safety labs	X																X ²
Physical examination	X																X
Epworth Sleepiness Scale	X																
Twelve-lead ECG ³	X																X
Vital signs ⁴	X	X	X		X	X		X	X			X	X		X	X	X
Temperature	X																X
Admission to clinic ⁵		X			X			X				X		X			
Discharge from clinic ⁶				X			X			X			X			X	
Study Drug Administration			X			X			X			X			X		
PK sampling ⁷			X			X			X			X			X		
CogScreen SDC Training/Practice	X	X			X			X				X		X			
Driving Sim Training/Practice	X	X			X			X				X		X			
Simulator Sickness Questionnaire	X																
KSS ⁸			X			X			X			X			X		

Self-Perceived Questionnaire (safe to drive)			X			X			X			X			X		
CVDA Drive			X			X			X			X			X		
VAS			X			X			X			X			X		
CogScreen SDC Test			X			X			X			X			X		
C-SSRS	X	X			X			X			X			X			X
Adverse event assessment	X	X	X	X	X	X	X	X	X	X	X	X	X	X	X	X	X
Concomitant meds assessment	X	X	X	X	X	X	X	X	X	X	X	X	X	X	X	X	X

¹ Height and BMI will be measured at Screening only.

² Safety labs (hematology, chemistry and urinalysis) at Screening and Day 35 or EOS only.

³ Twelve-lead ECG will be obtained at Screening and Day 35 or EOS only.

⁴ Vital signs will be collected at Screening, CRU check-in on Days -1, 6, 13, 20, and 27, pre-dose and 1.17 hours post dose on Days 1, 7, 14, 21, and 28, and at Follow-up/Day 35 or EOS.

⁵ Subjects will be inpatient on Days -1, 6, 13, 20, and 27.

⁶ Subjects will be discharged approximately 24 hours post-dose.

⁷ Plasma PK samples for lasmiditan levels will be collected at the following time-points: Days 1, 7, 14, 21, and 28 pre-dose (within 30 minutes before dosing) and 2.58 hours (155 minutes -15 to +30 minutes) post dosing.

⁸ KSS is performed before each drive.

⁹ A serum pregnancy test will be performed upon admission to the unit for females of child-bearing potential.

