14.3.4.4 Summary of Hematology

14.3.4.5 Summary of Quantitative Urinalysis

Table 14.3.5.1
Listing of Abnormal On-Study Vital Signs Values
(Safety Population)

Assessment (Units)	Subject ID/Gender/Age	Sequence	Visit	Elapsed Time	Position	Date / Time	Value	Change from Baseline	Safety Review
Vital Sign Test 1	xxx		xxxxxxx	xxxxxxx	xxxxxxx	YYYY-MM-DD:XX:XX	xxx	xxx	xxx
	xxx		xxxxxxx	xxxxxxx	xxxxxxx	YYYY-MM-DD:XX:XX	xxx	xxx	xxx
Vital Sign Test 2	xxx		xxxxxxx	xxxxxxx	xxxxxxx	YYYY-MM-DD:XX:XX	xxx	xxx	xxx
	xxx		xxxxxxx	xxxxxxx	xxxxxxx	YYYY-MM-DD:XX:XX	xxx	xxx	xxx
Etc.	xxx		xxxxxxx	xxxxxxx	xxxxxxx	YYYY-MM-DD:XX:XX	xxx	xxx	xxx

Date: VERSION - YYYY-MM-DD

Data Source: XXXX

Program Source: XXXXX.sas

Table 14.3.5.2
Listing of Clinically Significant On-Study Vital Signs Values
(Safety Population)

Assessment (Units)	Subject ID/Gender/Age	Sequence	Visit	Elapsed Time	Position	Date / Time	Value	Change from Baseline	Safety Review
Vital Sign Test 1	xxx		xxxxxx	xxxxxx	xxxxxx	YYYY-MM-DD:XX:XX	xxx		xxx
	xxx		xxxxxx	xxxxxx	xxxxxx	YYYY-MM-DD:XX:XX	xxx		xxx
Vital Sign Test 2	xxx		xxxxxx	xxxxxx	xxxxxx	YYYY-MM-DD:XX:XX	xxx		xxx
	xxx		xxxxxx	xxxxxx	xxxxxx	YYYY-MM-DD:XX:XX	xxx		xxx
Etc.	xxx		xxxxxx	xxxxxx	xxxxxx	YYYY-MM-DD:XX:XX	xxx		xxx

Date: VERSION - YYYY-MM-DD

Data Source: XXXX

Program Source: XXXXX.sas

Table 14.3.5.3
Summary of Vital Signs
(Safety Population)

Parameter (unit)	Visit	Timepoint	Statistic	Placebo (N=XX)	Lasmiditan 50 mg (N=XX)	Etc. (N=XX)
Vital Sign Test 1	Screening	Value	N			xx
			Mean (SD)			xx (xx.x)
			Median			xx.x
			Min, Max			xx, xx
	Day -1	Value	N	xx	xx	xx
			Mean (SD)	xx (xx.x)	xx (xx.x)	xx (xx.x)
			Median	xx.x	xx.x	xx.x
			Min, Max	xx, xx	xx, xx	xx, xx
	xxx	Value	N	xx	xx	xx
			Mean (SD)	xx (xx.x)	xx (xx.x)	xx (xx.x)
			Median	xx.x	xx.x	xx.x
			Min, Max	xx, xx	xx, xx	xx, xx
	Change from Baseline	N	xx	xx	xx	
		Mean (SD)	xx (xx.x)	xx (xx.x)	xx (xx.x)	
		Median	xx.x	xx.x	xx.x	
		Min, Max	xx, xx	xx, xx	xx, xx	
Etc.	Etc.					

PROGRAMMING NOTE: All visits outlined in Appendix A will be included.

Date: VERSION - YYYY-MM-DD

Data Source: XXXX

Program Source: XXXXX.sas

Table 14.3.6.1
Listing of Abnormal On-Study ECG Assessments
(Safety Population)

Subject ID/Gender/Age	Sequence	Visit	Date / Time	Position	Safety Review	Parameter (Unit)	Value	Change from Baseline
xxxxx		xxxxxx	YYYY-MM-DD: HH:MM	xxxxxx	xxxxxx			
			YYYY-MM-DD: HH:MM	xxxxxx	xxxxxx			
			YYYY-MM-DD: HH:MM	xxxxxx	xxxxxx			
xxxxx		xxxxxx	YYYY-MM-DD: HH:MM	xxxxxx	xxxxxx			

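### Vital-sign change is measured from one pre-study baseline and split by visit, so no planned table shows the same-morning post-dose change for all of about 80 subjects per dose

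*SAP*

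**What the plan says.** SAP section 6 (Analysis Time Points) gives the default: "Unless otherwise specified, the baseline value will be defined as the last non-missing evaluation prior to the first dose of study medication". The wording allows exceptions, but none is given for vital signs in SAP section 10, the shell for Table 14.3.5.3 or the listing shells.

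For vital signs, SAP section 10 says that "raw values, as well as the change from baseline, at each time point will be summarized by treatment, parameter and visit". Table 14.3.5.3 is the only planned summary table; Tables 14.3.5.1 and 14.3.5.2 list abnormal and clinically significant values. The shell has treatment columns and visit rows, and its note reads "PROGRAMMING NOTE: All visits outlined in Appendix A will be included". Appendix A schedules the readings "pre-dose and 1.17 hours post dose on Days 1, 7, 14, 21, and 28", and protocol section 10.2.2 agrees: "Vital signs will be measured pre-dose and at 1.17 hours after dosing".

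Protocol section 13.4.3 asks for the summary by dose and mentions no visit split: "Changes from baseline in vital signs will be summarized by descriptive statistics for each dose". SAP section 12 states: "There is no change from the planned analysis described in the protocol".

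**The concern.** In a single-dose crossover with a reading shortly before each dose, the natural measure of acute effect is the post-dose value minus that morning's pre-dose value, summarised over everyone who took the dose. The plan collects both readings but uses the same-morning pre-dose value as baseline only in Period 1. Later periods bring in day-to-day variation over one to four weeks, after one to four other study treatments.

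The visit split then divides each dose among five rows, and within any row the treatment columns hold different subjects. A reader of the report could not see the SD, median or range of the acute heart-rate or blood-pressure change for any dose without re-analysing the individual data. What is at stake is the precision and readability of a descriptive safety summary.

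**Working it through.** The documents give no cell counts, variances or correlations for vital signs, so there is no stated figure to reproduce. The inputs are the ten sequences and 80 planned completers (SAP section 3), the nominal dosing days 1, 7, 14, 21 and 28 (Appendix A), and the clock times in protocol section 10.3.

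**Age of the baseline.** If the Day 1 pre-dose reading is present, it is the baseline for the whole study.
- Period 1: vital signs at 8:00 and 9:40 are 100 minutes apart.
- Periods 2 to 5: 7 − 1 = 6, 14 − 1 = 13, 21 − 1 = 20 and 28 − 1 = 27 days.

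**Subjects per cell.** The SAP says "Subjects will be randomized equally into one of ten treatment sequences", so 80/10 = 8 per sequence. Counting the sequence table, each of the five treatments appears exactly twice in every period.
- Per treatment and dosing day: 2 × 8 = 16.
- Per treatment over five periods: 5 × 16 = 80.
- Per treatment in Periods 2 to 5, with an old baseline: 4 × 16 = 64, or 80%.

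**Effect of the layout**, in units of the SD of the change:

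| | n = 16 | n = 80 |
|---|---|---|
| SE = 1/√n | 0.250 | 0.112 |
| 95% half-width = t(0.975, n − 1)/√n | 0.533 | 0.223 |

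The SE ratio is √(80/16) = √5 = 2.24, taking the SD of the change as equal.

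**Effect of the baseline choice.** With equal variances at the two readings, the variance of a change is proportional to 1 − ρ. The variance ratio in Periods 2 to 5 is R = (1 − ρ_far)/(1 − ρ_near), and the SD ratio is √R. Period 1 is unaffected, so over all five periods the SD ratio is √((1 + 4R)/5). As an assumption, take ρ_near (same morning) as 0.70 to 0.85 and ρ_far (days to weeks apart) as 0.50 to 0.65.

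| ρ_far | ρ_near | R | SD ratio, Periods 2–5 | SD ratio, all periods |
|---|---|---|---|---|
| 0.65 | 0.70 | 0.35/0.30 = 1.17 | 1.08 | 1.06 |
| 0.50 | 0.70 | 0.50/0.30 = 1.67 | 1.29 | 1.24 |
| 0.65 | 0.85 | 0.35/0.15 = 2.33 | 1.53 | 1.44 |
| 0.50 | 0.85 | 0.50/0.15 = 3.33 | 1.83 | 1.69 |

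**What can be rebuilt.** Raw pre-dose and post-dose values are tabulated by treatment and visit. With complete pairs, the mean same-morning change is the difference of the cell means, and the five cells can be combined by hand. The SD, median, minimum and maximum of the paired change cannot be obtained that way.

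**The case against.** The strongest reply concerns the shell. Its Day -1 row is filled under the treatment columns, which makes sense only if days are counted within each period; on that reading each column would already hold about 80 subjects. But the note calls for all Appendix A visits, and these are numbered V1 to V17 on absolute study days, so the visit split is the better reading. Even on the other reading, the baseline in Periods 2 to 5 would still be the pre-first-dose value.

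Second, the protocol neither defines baseline nor forbids a visit split, and protocol section 13.4 asks for change at post-dose time points. This stands in part: the single baseline does not breach protocol text. However, presenting a post-dose time point does not require splitting by visit. The mismatch with section 13.4.3 is the absence of a pooled summary by dose.

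Third, a pre-first-dose baseline is drug-naive, raw values and listings are available, no confidence interval or test is planned for vital signs, and SAP section 13 permits extra tables. All of this is true and limits the weight of the point. But permission is not a commitment, and SAP section 6 labels any analysis performed after database lock post hoc and exploratory.

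**Conclusion.** The point holds. As written, the plan gives a same-morning change for about 16 of 80 subjects per dose, and no planned table pools it over periods. The layout result rests on 80 completers, equal sequence sizes and visit rows taken as study days; the five cells still contain all 80 subjects, so the loss is in display, not in data. The baseline effect depends on correlations the documents do not give, and is small at the low end of the assumed range.

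The drug-placebo contrast is not biased: placebo appears in the same visit rows and the sequences are balanced, so drift is equal in expectation. No SDLP or non-inferiority conclusion changes. This is a worthwhile correction to a descriptive safety summary, not a threat to the trial's main result.

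**What to change.** In SAP sections 6 and 10, define the baseline for post-dose change in blood pressure and heart rate as the pre-dose value of the same period. Summarise the 1.17-hour change by treatment, pooled over periods, with N, mean, SD, median, minimum and maximum. Revise the shell for Table 14.3.5.3 and the change columns in the vital-sign listings to match.

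The by-visit table and the change from the study-level baseline can stay as supplements. Laboratory tests, ECG, weight and temperature keep the study-level baseline.

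The cost is SAP and shell wording plus one summary. No new data are needed and nothing is lost. It should be done before database lock.
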